1.5 PRELIMINARY DATA

Over 10% of patients develop an AKI consistent with CIN after contrast-enhanced CT imaging. These patients are also at significantly increased risk of severe outcomes over the following year. In the largest cohort published to date, the PI and her collaborator ([name]), prospectively followed 633 unselected patients undergoing contrast-enhanced CT imaging for the outcomes of AKI consistent with CIN and 1-year major adverse outcomes including death, renal failure and cardiovascular events (stroke, myocardial infarction, other vascular events requiring

medical or surgical intervention). Notably, this is a larger cohort than that planned for the proposed study. The incidence of CIN was over 10% in all patients,²⁰ and 15% in the population undergoing CTPA.⁷ There was no difference in the rate of CIN among inpatients compared to patients discharged after imaging. After adjusting for age and comorbidities, the development of CIN was associated with a markedly increased risk of death (Figure 2)^{7,11,20} and an increased risk of major adverse events, including renal failure and arterial vascular events requiring intervention, at 1-year (adjusted RR 2.36 95%CI 1.5 to 3.7). The risk of severe outcomes increased with severity of AKI.^{11,20}

The study investigators have previously developed methods of identifying patients evaluated for PE that can be safely randomized: A co-investigator for this study ([name]) derived and validated an attribute matching method to individually quantify the pre-test probability of venous thromboembolism (VTE, PE or deep venous thrombosis [DVT]), PE PreTest Consult Score (PreTest Consult©; v2.1Q; CP Diagnostics, LLC; Charlotte, NC).^{47,56-59} (Figure 3) The PE PreTest Consult Score leverages prospective data from over 8,000 patients evaluated for PE, by CTPA or VQ, at 7 medical centers (6 in the United States and 1 in New Zealand) and is openly available

(<http://pretestconsult.com/v21/pe>). Importantly, this method of assessing pre-test risk of VTE is *well-accepted and used by physicians at medical centers throughout the United States.*¹²

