The 45-day incidence of VTE in patients with a calculated pre-test risk between 2.5% and 20% was 3%. Importantly, the accepted test threshold prompting imaging for suspected PE is very low: only 2.5%.^{13,48} As such, <15% of patients who underwent imaging for suspected PE ultimately were ultimately diagnosed with VTE. Pre and post-CTPA creatinine data were available for 30% of a validation subset (834 patients from 4 institutions)

[figure not shown]

Figure 3. Example output of the PE PreTest Consult Score (<http://pretestconsult.com/v21/pe>), which allows clinicians to calculate the point-estimate of an individual patient's pre-test probability of pulmonary embolism, at the bedside, using an attribute matching method leveraging over 2 decades of data, from over 8,000 patients evaluated at 7 medical centers, developed by a co-investigator ([name]) along with the PI.^{47,56-59}

[figure not shown]

Figure 2. Cumulative hazard plot for 1-year mortality for patients with and without Contrast-Induced Nephropathy (CIN), adjusted for age and the presence of an active malignancy at the time of enrolment. ($p < 0.01$).

evaluated simultaneously for both suspicion of acute coronary syndromes and PE. In patients at low and moderate risk of PE (pre-test VTE risk $\leq 20\%$), the rate of AKI consistent with CIN, did not differ with the presence (9%) or absence (8%) of a VTE.

The PI has developed methods of risk-stratifying patients for CIN in the emergency care setting: Using data from her contrast-enhanced CT cohort of patients treated in the emergency care setting, the PI evaluated over 100 literature derived risk factors (at varying thresholds) for CIN^{18,23,28,41,60-83} and derived the AKIrisk Score: 2 points for glycosuria on urine dipstick; and 1 point each for Age ≥ 50 years, measured diastolic blood pressure ≥ 100 mmHg, history of HIV or AIDS, and a history of coronary artery disease.⁸ Importantly, an elevated creatinine (SCr), corresponding to an estimated glomerular filtrate rate (eGFR_{SCr}) ≤ 60 ml/min/m²,¹⁷ did not accurately risk-stratify patients for CIN: sensitivity 13%, area under the receiver operating characteristic curve (AUROC) 0.55.^{9,10} In comparison, a AKIrisk Score of ≥ 2 points more accurately predicted CIN: sensitivity 56% (95% CI 43 to 68%), specificity 81% (95% CI 77 to 84%), AUROC of 0.74 (95% CI 0.68 to 0.81) and positive predictive value (27%, 95% CI 20 to 34%).⁸⁻¹⁰ (Figure 4)

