We acknowledge that the primary outcome of CIN is likely to occur in patients that remain asymptomatic, as expected for the first stages of AKI. We do plan to measure and report patient-center, symptomatic, severe outcomes (see *Secondary Endpoints*) occurring within 1-year. Aside from our own preliminary data,^{7,11,20} there are no consistent, published, prospective data, with sufficient long-term follow-up,^{32,45} in the emergency care setting, or other comparable heterogeneous, ambulatory population (pre-exposure renal function ranging from normal to impaired). Moreover, there are no prospective, controlled data, in any setting, that can be used to adequately design (and determine the sample size for) a study primarily aimed at measuring the long-term, severe outcomes subsequent to CIN. Hence, we have focused on the first phase of AKI, CIN, as the primary outcome, and plan to use the data to inform future research quantifying the effect of selected contrast media exposure on the prevention of long-term severe outcomes subsequent to the development of CIN.

To determine sample size, we conservatively estimated an overall AKI rate of <20%. The sample size was determined based on a Chi-square test (two-tailed, 5% type I error). A sample size of 188 in the CTPA group (exposed) and 269 in the VQ group (unexposed) in each group will have 80% power to detect an absolute difference of 10%. Assuming up to 5% screening and randomization failures (patients assigned to VQ, but undergo CTPA imaging) and a 30% dropout rate,^{7,11,20,53,89} we will recruit 300 subjects per group. (nQuery 2014; Statistical Solutions©)

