We will reject the null hypothesis and the two groups, CTPA and VQ, will be considered equivalent if

$$\frac{\hat{P}_1 - \hat{P}_2 - \delta}{\sqrt{\hat{P}_1(1 - \hat{P}_1)/n_1 + \hat{P}_2(1 - \hat{P}_2)/n_2}} < -z_{0.05} \quad \text{and} \quad \frac{\hat{P}_1 - \hat{P}_2 + \delta}{\sqrt{\hat{P}_1(1 - \hat{P}_1)/n_1 + \hat{P}_2(1 - \hat{P}_2)/n_2}} > z_{0.05}$$

If we reject the hypothesis of equivalency, we will conduct an analysis for a superior trial. Hence, for comparison with the dichotomous primary outcome, that is, whether a subject develops AKI at the 2-7 day follow-up, a logistic regression model will be used. Group comparisons will be adjusted for baseline covariates. To validate the decision rule in classifying subjects into a low-risk group we will: 1) Measure the AKI rate in the low-risk group (AKIRisk Score <2) with a desired margin of error. We assumed the upper limit of the one-way 95% confidence interval to be <10%, based on preliminary data, and prior literature.^{6,7} as such, we will compute the one-way 95% confidence interval using a Z test statistic; and 2) Compute sensitivity and specificity of the decision rule.

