Sample Size We will use a prospective validation study design for the previously derived decision rule (AKIrisk Score), classifying subjects into low AKI-risk group. We will recruit 100 subjects undergoing CTPA with an AKIrisk Score <2 . Since the overall AKI rate in our patient population of interest is $<10\%$ (see *Preliminary Data*), the group of subjects with AKIrisk Score <2 will have much lower AKI rate. Assuming 5% AKI rate in this low risk group, the upper limit of one way 95% confidence interval will be $\leq 9.3\%$ with a sample size of 100 (adjusted for dropout and screening failures).

Secondary Outcome Analysis: We will measure several secondary outcomes of which almost all are dichotomous (e.g. death, renal failure, stroke and/or other acute arterial vascular events). We will use a logistic regression model including the baseline covariates in the model. In case of rare events, we will use an exact logistic regression analysis. For the change in continuous outcomes, we will use ANCOVA model including the baseline covariates. Using similar analyses, we will compare baseline outcomes between enrolled subjects and subjects who will meet the inclusion criteria but decline participation in the study. Finally, we will compare outcomes of patients, relative to the AKIrisk Score, and we will compare outcomes and demographic data of those who enroll versus those who meet inclusion but decline participation to assess for possible bias induced by the informed consent process.⁸⁴

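### The 9.3% upper limit planned for the low-risk (AKIrisk <2) group is a normal-approximation bound on about 3.5 expected events; Wilson and exact bounds give 11.2% and 11.7%, so 10% would not be excluded.

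*Combined protocol and SAP*

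**What the plan says.** The sample-size paragraph of section 2.2 recruits 100 patients with an AKIrisk Score below 2 and states: "Assuming 5% AKI rate in this low risk group, the upper limit of one way 95% confidence interval will be" at most 9.3%. It describes the 100 as already allowing for dropout and screening failures, but gives no number evaluable.

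The method is in section 2.1, Primary Outcome Analysis: "we will compute the one-way 95% confidence interval using a Z test statistic". The target is there too: "We assumed the upper limit of the one-way 95% confidence interval to be <10" percent. Aim 1 in section 1.2 is the claim that this bound serves, a risk below 10% when the score is below 2.

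The loss rates appear only in the sample-size text for the randomized comparison in section 2.1: "Assuming up to 5% screening and randomization failures (patients assigned to VQ, but undergo CTPA imaging) and a 30% dropout rate".

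The 5% assumption rests on a premise about the whole population, which begins "Since the overall AKI rate in our patient population of interest is" and puts that rate below 10%, citing the preliminary data. Section 1.5 gives two different pictures. For the 633-patient CT cohort, "The incidence of CIN was over 10% in all patients", and it was 15% among those having CTPA. For patients with a pre-test risk of 20% or less, "the rate of AKI consistent with CIN, did not differ with the presence (9%) or absence (8%) of a VTE"; those data come from a subset of 834 patients, of whom 30% had creatinine values before and after CTPA.

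**The concern.** A bound of the form estimate plus 1.645 standard errors behaves badly when only three or four events are expected. It sits too low, and when few events are seen it shrinks towards zero. Here the error runs towards calling patients low-risk, which is the claim under test.

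The bound is the decision statistic for Aim 1. If it is too narrow, the score could be declared to identify patients with a risk under 10% on data that do not establish this at the stated confidence. The planning figure would also give a misleading picture of how likely the criterion is to be met.

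The Secondary Outcome Analysis paragraph in section 2.2 shows awareness of small counts: "In case of rare events, we will use an exact logistic regression analysis". Nothing similar is planned for this single proportion.

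**Working it through.** **Inputs.** Assumed rate 5%, one-sided 95%, 100 recruited with attrition allowed for (section 2.2); dropout 30% (section 2.1); threshold 10% (sections 1.2 and 2.1). Evaluable number: 100 × (1 − 0.30) = 70. Expected events: 70 × 0.05 = 3.5.

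**Reproducing the plan's figure.** One-sided Wald bound:

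p + 1.645 × √(p(1 − p)/n) = 0.05 + 1.645 × √(0.0475/70) = 9.28%.

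Solving the same formula for a limit of 9.3% gives n = 69.5, which supports 70. A two-sided multiplier of 1.96 with all 100 evaluable also gives 9.27%, but that fits neither the one-sided wording nor the attrition allowance.

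**Other bounds at 5% of 70.** With z = 1.645:

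- Wilson: [p + z²/2n + z√(p(1 − p)/n + z²/4n²)] / (1 + z²/n) = 11.20%.
- Clopper-Pearson: the 95th percentile of Beta(x + 1, n − x), taken at x = 3.5, is 11.66%. The half event is an interpolation; whole counts follow.

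**Upper limits by event count, n = 70**

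| Events | Wald | Wilson | Exact |
|---|---|---|---|
| 2 | 6.1% | 8.3% | 8.7% |
| 3 | 8.3% | 10.2% | 10.7% |
| 4 | 10.3% | 12.1% | 12.6% |

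The Wald limit is below 10% with 3 or fewer events. Wilson and exact need 2 or fewer.

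**Coverage at a true 5%, n = 70.** The Wald limit misses 5% when 0 or 1 event occurs (limits 0% and 3.8%): coverage = 1 − P(X ≤ 1) = 87.1%. Wilson and exact miss only at 0 events: 97.2%.

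**Decision properties, binomial with n = 70**

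| True rate | P(X ≤ 3), Wald rule | P(X ≤ 2), Wilson or exact rule |
|---|---|---|
| 10% (false claim, nominal 5%) | 7.1% | 2.4% |
| 5% (planning assumption) | 53% | 31% |

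**Other evaluable numbers.** At 65, 66, 67, and 70 to 100 in steps of 5, the Wald rule's false-claim rate at a true 10% runs from 6.4% to 11.9% (11.7% at n = 100). The exact rule stays at or below 4.7%. With 5 events in 100, the limits are Wald 8.6%, Wilson 9.9% and exact 10.2%.

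**Is 5% a central assumption?** Section 1.5 gives sensitivity 56% and specificity 81% for a score of 2 or more. If these carry over, the rate in the low-risk group at an overall rate π is

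0.44π / [0.44π + 0.81(1 − π)].

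| Overall rate | Low-risk rate |
|---|---|
| 8% | 4.5% |
| 9% | 5.1% |
| 10% | 5.7% |
| 15% | 8.7% |

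From 4.5% to 8.7%, the chance that the exact or Wilson limit falls below 10% drops from 38% to 5% at 70 evaluable (Wald: 61% to 13%).

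**The case against.** Five points deserve an answer.

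- **Other small-sample bounds side with Wald at 3/70.** Mid-P gives 9.91% and Jeffreys 9.73%, both below 10%. The figures are right. But any rule that accepts 3 events in 70 makes a false claim 7.1% of the time at a true 10%, so at this number those bounds also miss the nominal 5%.
- **The replacement is conservative.** It errs at 2.4% rather than 5% and lowers the chance of success at a true 5% from 53% to 31%. This stands, and is a cost to state openly. It is an error in the safe direction for a low-risk claim.
- **The analysis text does not say Wald.** Inverting a one-sample Z test with the variance under the null gives the Wilson bound. On that reading, though, the planning figure should be 11.2%, and the stated 9.3% is wrong. One of the two passages has to change.
- **The 70 is inferred.** The 30% dropout is given for the randomized groups, and section 2.1 allows multiple imputation if missing values threaten power. With all 100 evaluable, Wilson at 5 events (9.9%) does exclude 10%. That stands as a qualification for Wilson; the exact bound does not exclude it (10.2%), and full retention does not repair the Wald rule's false-claim rate.
- **The premise below 10% can be defended.** The 8–9% in section 1.5 belongs to the eligible pre-test stratum. The 8.7% end of the range combines the 15% CTPA rate with accuracy figures from a cohort of all contrast CT. Solving section 1.5's own 56%, 81% and positive predictive value of 27% together gives about 11% overall and 6.4% in the low-risk group. So the premise is not shown to be false, but its source needs naming.

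The exact logistic regression planned for rare events is a model for other outcomes. Not using it here is no contradiction. The aim is secondary, and the randomized comparison is untouched.

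**Conclusion.** The concern holds. The 9.3% is computed correctly for a one-sided Wald interval at 70 evaluable patients, but that interval understates the uncertainty with about 3.5 expected events: coverage at a true 5% is 87.1%, and at a true 10% the false-claim rate is 7.1% instead of 5%. Bounds suited to small counts give 11.2% to 11.7% at the assumed rate, so the planned sample would not exclude 10% if the observed rate matched the assumption. A result of 3 in 70, next to the expected count, would pass or fail Aim 1 according to the interval used.

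This rests on 70 evaluable, which is inferred from the stated dropout and supported by back-solving the plan's figure. The excess false-claim rate of the Wald rule does not depend on it, as it appeared at every number checked from 65 to 100. The further finding that 5% lies near the favourable end of 4.5–8.7% assumes that the score's published sensitivity and specificity carry over to this population.

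**What to change.** - **Section 2.1, Primary Outcome Analysis:** replace the Z-based limit with a one-sided 95% Clopper-Pearson upper bound, or a Wilson bound if preferred, named before data are seen.
- **Section 2.2, sample size:** state the number evaluable and the loss rate assumed for this non-randomized group. If that is 70, give the upper limit at an observed 5% as about 11–12%, and say that 2 or fewer events are needed to fall below 10%.
- **Same paragraph:** name the source of the overall rate below 10% (the stratum with pre-test risk of 20% or less, or the CT cohort). Give the implied low-risk range of about 4.5–8.7% with the matching chance of meeting the criterion, 38% down to 5% at 70 evaluable.

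The change is to wording only and needs no extra patients. Its cost is a less favourable planning statement and, at 70 evaluable, a conservative bound.

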Figure 1. The direct nephrotoxicity of contrast agents has decreased while exposures have dramatically increased. Contrast-enhanced CT imaging, particularly from the emergency care setting, is now the major source of patient exposures to contrast media agents.

Despite a lack of definitive evidence, significant effort and costs are associated with both the prevention and treatment of CIN. Precedent literature attributes CIN with marked increases in hospital mortality, prolonged hospitalization and increased costs.^{1,33,34} Over one quarter of all laboratory testing in the emergency care setting alone is performed with the express purpose of identifying patients at increased risk of CIN.³⁵ National and international cardiology and radiology organizations continue to invest resources into developing and promoting national guidelines aimed at reducing CIN.³⁶⁻⁴² However, research aimed at quantifying the potential impact of reducing contrast media exposure is limited to a single active meta-analysis protocol.³⁰ There are no active, randomized trials that address this long-standing controversy. (www.clinicaltrials.gov, accessed 3/10/2015).

The following conditions are necessary for a trial of this type:

- 1) Prospective Design: With CIN, the characteristic rise in creatinine does not peak for 3 to 5 days, or longer in more severe cases.^{43,44} Similarly, the change in creatinine needed to identify other causes of AKI is variable. Moreover, routine, compulsory post-exposure surveillance for AKI is not currently the standard of care, or even common practice, especially in the outpatient and reduced-hospital stay settings. As such, retrospective, post-exposure data are likely to severely and unpredictably underestimate both the relative contribution of CIN and other causes of AKI.^{14,16,32,45}
- 2) Controlled, Randomized Exposure: Contrast media is administered for specific clinical indications; populations undergoing contrast-enhanced and non-contrasted diagnostic studies are distinct, and differ significantly in terms of acute illness state and risk of CIN or other AKI. Thus, unstructured comparisons between these populations are severely limited.
- 3) Comparison of Clinically Equivalent Diagnostic Imaging Tests: The standard contrast-enhanced study(ies) and the non-contrast alternative(s) must have equivalent diagnostic accuracy and cannot carry significantly higher risk of adverse events (e.g. radiation exposure, invasiveness, etc.).

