1.6 Known Potential Risks

400 patients enrolled in this study will go on to complete the CTPA (300 with a AKIrisk Score ≥ 2 after random assignment and 100 with a AKIrisk Score < 2) and, as ordered, and will have an exposure to contrast media as a result of usual care. The remaining 300 patients will undergo VQ imaging, which has equivalent diagnostic accuracy for PE (in patients with a pre-imaging risk of PE $\leq 20\%$ and a normal chest radiograph) and the same or lower risks of exposure to ionizing radiation as CTPA.^{50,53,54} Patients may provide a urine sample and could have as many as two blood draws, which is associated with minimal risk. Importantly, these patients will already have intravenous access placed in preparation for the diagnostic imaging, as part of their usual medical care. Thus, for the majority of patients, the first blood sample may not require an additional needle stick.

The decision of whether or not to enroll could induce psychic stress to the patient at a time when they are already afraid. The PI and co-investigator ([name]) have conducted telephone follow-up with patients treated in the emergency care setting as proposed here on over 4,000 patients with no patient complaints or evidence of distress.^{11,20,47,103} From prior experience, we estimate that 60% of patients will have primary family members present at the time of informed consent. Patients will be informed on the potential increase in time spent in the emergency department during the informed consent process. There may also be a potential loss of confidentiality. Clinical data will be collected by trained study personnel who are listed on the IRB approved protocol and all data will be kept in a secure electronic format. The PI, research coordinator and data analyst. Research assistants will have limited access and only as needed to assist with screening, enrollment, and coordination of follow-up. We will redact PHI from records that might be examined by non-study personnel.

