1.7 Known Potential Benefits

All patients enrolled in this study would have otherwise undergone CTPA imaging as a part of their usual care. Approximately half of patients enrolled ($n = 300$) will undergo VQ imaging which is associated with a risk of exposure to is comparable and potentially lower than that of CTPA^{50,53,54} but avoids an exposure to iodinated contrast media. Given the significant long-term consequences of even a single episode of CIN,^{11,28} the benefit may be improved methods of identifying patients at risk, and then preventing CIN and subsequent severe outcomes. Published data suggests that VQ may also decrease the risk of hemorrhage from unnecessary exposure to long-term anticoagulant therapy, as a result of over-diagnosis of small subsegmental PE.⁴⁹⁻⁵² At minimum, prior published data clearly demonstrate that the risk of missed VTE with VQ (and selective US) is not increased over CTPA.⁴⁹⁻⁵² Our preliminary data are consistent with published results. In addition, VQ imaging is associated with the same risk of exposure to ionizing radiation as CTPA, but avoids exposure to iodinated contrast media. Thus, patients participating in this study will undergo one of two standard of care imaging studies for PE. Patients who choose not to participate will undergo CTPA testing as planned. Participants will have the opportunity to complete CTPA imaging as planned or undergo VQ imaging, which has the same, or potentially less overall risk than CTPA. All patients will have the opportunity for post-imaging surveillance for AKI, which is not routinely performed. Patients who do develop AKI, based on follow-up creatinine screening at 2-7 days, will have the opportunity to seek follow-up care.

2. Study Objectives

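### The outcome comparison of enrolled patients with eligible decliners mixes consent with imaging type and ascertainment, so it cannot be read as a check on consent bias

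*Combined protocol and SAP*

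**What the plan says.** Section 2.2 (Secondary Outcome Analysis) plans two comparisons of enrolled patients with eligible patients who decline. One is at baseline: "we will compare baseline outcomes between enrolled subjects and subjects who will meet the inclusion criteria but decline participation in the study". The other adds outcomes, to assess bias from the consent process: "we will compare outcomes and demographic data of those who enroll versus those who meet inclusion but decline participation". The paragraph opens with "We will measure several secondary outcomes of which almost all are dichotomous (e.g. death, renal failure, stroke and/or other acute arterial vascular events", which gives examples and not a closed list. It does not say which outcomes enter the decliner comparison, does not restrict enrolled patients by imaging type, and does not say how decliners' outcomes will be collected.

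Elsewhere the protocol fixes what each group receives.

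- Imaging of decliners (section 1.7): "Patients who choose not to participate will undergo CTPA testing as planned".
- Imaging of enrolled patients (section 1.6): "400 patients enrolled in this study will go on to complete the CTPA", made up of 300 randomised patients with a score of 2 or more and 100 patients with a score below 2. Then: "The remaining 300 patients will undergo VQ imaging".
- Follow-up (section 4.1): the 2-7 day creatinine, the interviews and permission to obtain follow-up records are agreed to through informed consent. The waiver in that section is described in connection with identifying patients.
- Adjudication (section 2.2): secondary outcomes are judged from the medical record and interview responses. Reviewers do not see creatinine values measured only for the study. Renal failure uses the highest creatinine in the medical record.

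**The concern.** A check on consent bias needs two groups that differ in consent and, as far as possible, in nothing else that affects the measured outcome. Here two other differences are built in.

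1. **Exposure.** Decliners are planned for CTPA, while a large share of enrolled patients have VQ. Whether contrast changes AKI risk is the trial's own question, so the difference cannot be assumed harmless.
2. **Ascertainment.** Enrolled patients have a scheduled creatinine and interview; decliners have only what routine care records. Section 1.4 itself warns that "retrospective, post-exposure data are likely to severely and unpredictably underestimate both the relative contribution of CIN and other causes of AKI".

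The stake is the trial's statement about representativeness. A gap in outcomes could be taken as evidence that consent selected an unusual sample, or the absence of a gap as reassurance. Neither inference would be justified.

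**Working it through.** The plan gives no rate, sample size or effect for this comparison, so there is no figure to reproduce. The arithmetic below only shows how far the two built-in differences could move an AKI comparison when consent itself has no effect.

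**Imaging mix** (section 1.6)

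- VQ share of all enrolled: 300/700 = 42.9%.
- VQ share of enrolled with score 2 or more: 300/600 = 50%.
- VQ share of enrolled with score below 2: 0 of 100.
- VQ share of decliners: 0, if section 1.7 is followed.

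**Model for score 2 or more**

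- pC and pV are the true AKI risks after CTPA and VQ; f is the share of decliners' AKI cases that routine records capture.
- Enrolled, fully ascertained, 1:1 allocation: (pC + pV)/2.
- Decliners as observed: f × pC.
- Artefact, decliner minus enrolled: f × pC - (pC + pV)/2. It is zero at f = (pC + pV)/(2 × pC).

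**Inputs**

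- Risks: 32%/6% from Table 3 in section 1.5; 20%/10%, an assumption built on the 10-point difference and the ceiling of 20% in section 2.1; and 20%/20%, in line with the study hypothesis of no contrast effect.
- Capture f is an assumption. The value 0.30 is borrowed from section 1.5 ("Pre and post-CTPA creatinine data were available for 30% of a validation subset"), 0.65 from the admission rate in section 4.1, and 1 is complete capture.

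| pC / pV | Enrolled mix | f = 0.30 | f = 0.65 | f = 1 | Zero at f |
|---|---|---|---|---|---|
| 32% / 6% | 19.0% | 9.6 - 19.0 = -9.4 | 20.8 - 19.0 = +1.8 | 32.0 - 19.0 = +13.0 | 0.59 |
| 20% / 10% | 15.0% | 6.0 - 15.0 = -9.0 | 13.0 - 15.0 = -2.0 | 20.0 - 15.0 = +5.0 | 0.75 |
| 20% / 20% | 20.0% | 6.0 - 20.0 = -14.0 | 13.0 - 20.0 = -7.0 | 20.0 - 20.0 = 0 | 1.00 |

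Differences are in percentage points. The two mechanisms pull in opposite directions: CTPA for all raises the decliners' AKI if contrast matters, and thinner surveillance lowers what is observed.

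**Incomplete follow-up of enrolled patients.** Section 2.1 allows for 30% dropout. If dropouts count as no AKI, the enrolled figure is multiplied by 0.7.

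- 32%/6%: enrolled 0.7 × 19.0 = 13.3%; artefact 9.6 - 13.3 = -3.7 at f = 0.30 and 20.8 - 13.3 = +7.5 at f = 0.65.
- 20%/20%: enrolled 0.7 × 20.0 = 14.0%; artefact 6.0 - 14.0 = -8.0 at f = 0.30 and 13.0 - 14.0 = -1.0 at f = 0.65.

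**Equal ascertainment only.** With medical-record data in both groups but all randomised patients kept, the remainder is f × (pC - pV)/2. For 32%/6% this is 13 × f: 3.9 points at f = 0.30 and 13.0 at f = 1. For 20%/10% it is 5 × f: 1.5 and 5.0. For 20%/20% it is 0.

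**Equal ascertainment and same imaging.** f × pC - f × pC = 0 at any f, provided f really is the same in both groups.

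**The case against.** The strongest reply is that section 2.2 never says AKI will be compared with decliners. The outcomes it names are death, renal failure, stroke and arterial events. These are adjudicated from the medical record and interviews, and study-only creatinine is withheld from reviewers for enrolled patients too. The missing study creatinine therefore matters mainly for the primary, CIN-type endpoint. This stands, and it narrows the point. It does not remove it: the list is only of examples, AKIN stages 1-3 are also to be reported, reviewers see interview responses that decliners do not have, and the imaging mix affects any outcome that contrast might influence. Section 6.0 also has enrolled patients who meet the CIN definition notified and told to seek care, which can generate record entries that decliners would not have.

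A reader might infer that the comparison is bound to show a large spurious AKI deficit in decliners. The documents do not support that. The mechanisms oppose each other and can cancel. The 30% capture figure is creatinine availability in a different cohort, evaluated for both acute coronary syndromes and PE. Counting absent values as no AKI is an assumption, not a rule in the plan.

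A reader might also infer that the plan has no other evidence on selection, or that using decliners' records is unauthorised. Neither follows. Demographic and baseline comparisons are already planned, and section 4.1 adds a check against imaging logs after three months. The full scope of the waiver is not shown, and consent pages were removed from the text available here. What can be said is that the route to decliners' outcome data is not stated.

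**Conclusion.** The point holds for the outcome part of the comparison. As written, consent is confounded with imaging type and with ascertainment, so neither a difference nor its absence can be read as consent bias. The sign and size of the artefact cannot be determined from the documents. The AKI range of about -14 to +13 points assumes a score of 2 or more, full ascertainment of enrolled patients, the three risk pairs shown and f between 0.30 and 1. It is an illustration, neither a bound nor a forecast. For outcomes adjudicated from the medical record the ascertainment problem is smaller, but imaging mix and interviews still differ. For patients with a score below 2, all enrolled patients have CTPA and only ascertainment differs.

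The demographic and baseline comparisons are sound. The randomised comparison, the primary endpoint and the sample size are not touched. This is a cheap improvement to an exploratory check.

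**What to change.** In the Secondary Outcome Analysis paragraph of section 2.2:

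1. Make the demographic and baseline comparison the main check on consent bias.
2. Name the outcomes to be compared with decliners.
3. For outcomes, compare decliners only with enrolled patients imaged by CTPA in the same AKIrisk Score group. Defining that group by assignment to CTPA keeps out the few VQ patients who go on to CTPA (expected below 5%).
4. Ascertain outcomes from the medical record alone in both groups, excluding study-only creatinine and interview data. If AKI is included, report the share of each group with a post-imaging creatinine on record, because equal capture is an assumption and the notification in section 6.0 could disturb it. AKI need not be dropped.
5. State the source of decliners' outcome data and confirm that the waiver covers their follow-up records.

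The cost is a few lines of SAP wording, and ethics-board wording if the waiver does not already extend to follow-up. The enrolled comparator shrinks from 700 to 400 overall, and from 600 to 300 among those with a score of 2 or more. Rates from routine records will understate AKI in both groups, so they support a comparison but not an estimate of absolute incidence.
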